## **Participant Safety Procedures**

If the research interviewer hears about or sees that the participant intends to harm themselves or someone else, s/he will tell a doctor or some other authority so that they can get some help, even if it means telling the authorities without the participant's permission. In such a situation, the researchers would only disclose information that would prevent harm to the participant or other people believed to be in danger.

If we hear about or see something that would immediately endanger the participant or others, such as child abuse, we will seek help, to protect the child. If a participant tells us information about child abuse,

physical abuse or sexual abuse we must disclose this information to the appropriate individuals and/or authorities. We must report this information regardless of when the child abuse occurred (whether it is occurring now or happened in the past) or who was the victim of the abuse (whether it was the participant or someone else). Also, the researchers will report certain diseases that can be given to other people.

### **Study Procedures**

#### **1. Procedures Associated with the EFFECTIVENESS TRIAL:**

We will complete a randomized trial (N=250) comparing participants assigned to the Living Well self-management intervention or a medical illness education and support comparison group. Using an intent-to-treat framework, we will collect data from every participant time of consent, as well as at times of randomization, post-treatment (3 months from randomization assessment), and again 3 months later (6 months from randomization).

Services data regarding use of the ER and other medical services including outpatient appointments with primary and specialty care medical providers within the VA will be collected at the follow-up assessment (6 months from randomization) as this allows for a more realistic timeframe for assessing effects on service utilization. To inform related analyses we will also collect retrospective service utilization data for a full six months before time of consent.

#### **Procedures defining the consent, randomization, post-treatment and 6 month follow-up Veteran assessments:**

All participants will complete assessment interviews at the time of consent, randomization post-intervention (3 month post-randomization), and 3 months post treatment (6 months from randomization). Trained RAs blind to the participant's condition assignment will administer all assessments. In order to ensure that the assessors remain blind, the RA completing the randomization interview (who then informs the participant of their treatment condition) will not complete the post-treatment or 3-month post-treatment follow-up interview with that same participant. However, the post-treatment and 3-month post-treatment follow-up interview may be completed by the same RA. Prior to starting the post-treatment and 3-month post-treatment follow-up, participants will be told not to reveal their study condition (Living Well or medical illness education and support group). If they do, the RA will make a note in the interview materials indicating that the blind was compromised and at what point during the interview this occurred. This RA will still complete the rest of the interview with the participant. If the blind does become compromised, a different RA will conduct the next scheduled assessment. Interviews will take approximately 1 ½ to 2 hours to complete. Please see Detailed Description of Measures section of this protocol for list of assessments and interviews included in the follow-ups.

If study staff is unable to contact enrolled participants by telephone to schedule a randomization, post-intervention, or 3 month post-treatment interview, a letter will be sent to participants to let them know we are attempting to contact them.

Also, we will include CPRS/Chart Summaries of Medical ER Use and Prescribed Medications: CPRS extracted chart data (including admission and discharge codes) will be extracted and used to summarize rates, patterns and reason for visit for the six month interval post randomization. The decision to look at this for a full six months in lieu of immediately post-treatment was made in order to allow for a more realistic timeframe for assessing intervention effects on service utilization. We will also extract details regarding both psychiatric and somatic medications.

## **Procedures Defining the Delivery of the Experimental and Control Condition Interventions:**

### **Living Well (Experimental Condition):**

Living Well will be implemented as a 12 session small-group intervention (4-8 persons). Groups will meet weekly for 75 minutes for three months (12 sessions). The 12 session weekly curriculum will be delivered as a series of 4 three-session modules. Module one provides an overview of the full course and begins with a review of the key concepts of self-management and proceeds with sessions focused on learning the behavioral action planning and problem solving skills that are used across the remaining modules. Since the first module of this intervention contains the fundamental building blocks that will be utilized throughout the intervention, participants who miss any of the first 3 start-up sessions will be offered an opportunity to meet individually with a facilitator to review the missed session content. These review sessions can be completed by the participant either in person or by phone. Remaining modules focus on a variety of wellness topics including health eating, medication management, and communicating with providers. After completing the 12 weekly groups, participants will return to complete once monthly booster group sessions for the next three months. All Living Well group sessions and booster sessions will be video recorded. The Living Well intervention will be led by a trained interventionist and co-facilitated by a peer provider using the manualized curriculum developed in our previous research. The pairing of a trained peer and professional affords maximal flexibility and will help support uptake of the intervention. This study is based on the intent-to-treat model. Regardless of level of participation in the Living Well groups, all randomized participants will be eligible and contacted to schedule post treatment follow-ups for this study.

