### **Medical Illness Education and Support Group (Comparison Condition):**

We selected a comparison condition that would provide parallel focus (i.e. medical illness) but not include use of the core ingredients undergirding the Living Well intervention including behavioral action planning, problem solving, in-session and between session practice using specific disease self-management techniques and involvement of peer co-facilitators to enhance modeling and improve self-efficacy and activation. As with Living Well, the content of the intervention will have broad applicability across diverse chronic disease conditions. The comparison condition will be a once-weekly support and education group focusing on living with a chronic medical condition. All Medical Illness Education and Support group sessions will be video recorded. Groups will be led by a single professional interventionist and will include standardized didactic review of common challenges experienced by those living with a wide range of chronic medical illnesses and related behavioral and lifestyle self-management techniques. Each session will follow a basic structure that includes a review of the material presented in the previous session, new education content and discussion. This study is based on the intent-to-treat model. Regardless of level of participation in the Medical Illness Education and Support group, all randomized participants will be eligible and contacted to schedule post treatment follow-ups for this study.

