To maximize the use of modeling and optimize peer support, all peer providers will have a co-occurring chronic medical condition. Non-peer co-facilitators will be selected from our pool of research interventionist all of whom have prior experience conducting psychosocial interventions with individuals with serious mental illness. If possible, we will select those who are living with a chronic medical condition to further maximize the effects of modeling and support based on a shared experience. To aid with ongoing supervision and fidelity monitoring, we will develop a structured supervision strategy that includes audio/videotaping of all session, weekly supervision conducted by one or more of the investigators, and objective assessment of adherence and competence. To complete this aspect of fidelity assessment we have developed a facilitator adherence and competence rating scale. The adherence scale contains items (scored "excellent," "acceptable" or "unacceptable") assessing the presence or absence of core features of the intervention including instruction in and practice behavioral action planning, in-session practice of self-management techniques, and use of problem solving. The Competence scale contains items assessing more process-oriented aspects including effective use of peer modeling, use of confidence building techniques, and reinforcement and encouragement of self-management skills. Ratings will be completed by an independent rater from a randomly selected 25% of each peer/provider pair's audio/video-recorded sessions. A second rater, will independently rate a subset

of the tapes to assess inter-rater reliability. Both of these raters will be study staff directly involved with this project and listed on the protocol.

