### **Sample Size**

For EFFECTIVENESS TRIAL:

This Randomized Controlled Effectiveness Trial is powered to detect differences on the two primary outcomes: (1) significantly reduced proportion of participants with an ER visit at the 3-month follow-up assessment (6 months post randomization) in the Living Well condition versus control, (2) significantly improved health functioning at post-treatment in the Living Well condition versus control as measured by the SF-12.

ER Visits. In our prior pilot the proportion with an ER visit in the Living Well condition at the 3-month follow-up was 10.7% and in the control condition it was 27.6%. For this power calculation we assumed that the proportion with an ER visit in the Living Well condition at the 3-month follow-up will be 10.7%. However, since we have an active control in this proposal, we specify a lower percentage in the control condition (versus estimate from the pilot study) equal to 25%, and thus a 14.3 percentage point difference. With a two-tailed, alpha .05 level test, and power = .80 to detect this 14.3 percentage point difference we calculate that we will need n = 250 (125 per condition). The percentage point difference that can be detected could be somewhat higher or lower depending on the inter-correlations among the covariates and ER response variable. As proportion with an ER visit will be obtained from VA electronic medical charts for all randomized participants, loss to follow-up is not a significant concern for this outcome. This calculation is conservative -- we would actually have power equal to .80 to detect a smaller difference because the above calculation is based on a basic z-test of proportions, whereas the analysis model

specified above is more powerful. Calculation was performed using PASS version 11.0 (from NCSS, LLC) software. We acknowledge that use of the ER may be different in the VA context given the co-location of medical and psychiatric care, but as evidenced in our previous work (see section A.3), we found that veterans with SMI used the VA ER for medical care at rates comparable to (even greater than) those in our community sample. Specifically, the rate of use in the VA sample was 43% and the baseline rate in the Living Well sample was 31.3%.

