SF-12 functioning scales. Effect sizes (ES, Cohen's d at post-treatment--3 months post-randomization) in our pilot clinical trial for the SF-12 physical, emotional, and general functioning scales were .55, .66, and .68. For H1 we assume a consent sample size equal to the sample size determined for H2 and calculated the power we will have to detect a moderate but significant ES = .40 (i.e. to detect means that are .4 standard deviations apart) between Living Well and the control condition. ES = .40 was also selected as the ES for this trial may be smaller than our prior trial because we are using an active control. We assume there will be 12% loss-to-follow-up at the post-treatment assessment, hence we have conservatively assumed a net sample size of  $250 * (1 - .12) = 220$  (110 per condition) for the SF-12 outcomes. With a two-tailed, .05 alpha level test, and average correlation among longitudinal measurements equal to .50, and post-attrition n = 220, we would have power = .89 to detect an effect size equal to .40. Calculation was performed using the Sampsii command (for repeated measures) in Stata version 10 (from Stata Corporation).

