#### Data Analysis

##### FOR EFFECTIVENESS TRIAL:

Primary Hypotheses (regarding functional and service-related outcomes):

Hypothesis 1 (H1): Compared to those receiving a general medical illness education and support group, participants receiving Living Well will demonstrate greater improved general health functioning including both physical and emotional functioning.

To test the null hypothesis of no difference in improved general health functioning, we will use a longitudinal mixed effects model to compare change in mean physical and emotional health functioning from randomization to post-treatment. Regression equation (random effects not presented) at each time point will be:

SF12 function = Intercept + site + covariates + study condition + time + study-condition\*time + error

Notes: (1) Test of the null hypothesis of no difference in change from randomization to the post-treatment assessment will be conducted using a specified contrast. (2) "Study condition" is a dichotomous variable indicating study condition; (3) A random intercept and random slope (coefficient for time) will also be specified for the model; (4) The "time" variable will be entered as a continuous variable with possible values 0, 3, and 6 corresponding to the three assessment points (randomization, post-treatment, & 3-month follow-up); (5) The "covariates" terms represent adjustment for age, race, gender, and important potential confounders and will include Charlson comorbidity index score, chronic somatic illness

category, and any other covariate found to significantly differ at randomization (provided no significant collinearities are found). We are expecting few chance differences at randomization due to large sample size and random study condition assignment; (6) We have included a “site” term to adjust for site differences.

Hypothesis 2 (H2): Compared to the medical illness education and support group, the Living Well group will have a lower proportion of participants who will have had an emergency room visit for management of a chronic medical condition during the six months after randomization.

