For proportion with ER use in the past 6 months, we will use a random intercept mixed effects model since this outcome is assessed at only 2 time points. We will use a model that assumes no difference at randomization given the large sample size and randomization to study condition. Thus we will not include study condition as a main effect which would correspond to an assumption of unequal randomization rate of ER use. Some chance variation is expected and we will test the assumption of equal randomization rates with a chi-square test comparing the ER use rates by study condition. This model is equivalent to adjusting for randomization in the continuous case and we are taking this approach to be able to have .80 power to detect a smaller percentage point difference in ER use (50) at the 3 month follow-up assessment than if we didn’t assume equal rates at randomization. In the very unlikely scenario of a statistical difference at randomization we will add the study condition main effect to the model below, and the test of the null for H2 will continue to be the test that the coefficient for the study-condition-by-time interaction term is zero. To compare the two conditions on probability (p) of an ER visit, we let the outcome variable  $Y = 1$  if the participant had an ER visit in the prior 6 months (at randomization or at 3-month follow-up) and  $Y = 0$  if participant did not have an ER visit. Analysis model (logistic mixed effects model, random intercept not displayed) will be:

$$\text{logit}(E[Y]) = \text{Intercept} + \text{site} + \text{covariates} + \text{time} + \text{study-condition} \cdot \text{time}$$

where  $E[Y] = p = \text{probability participant has an ER visit in the prior six months at either randomization or 3 month follow-up (depending on “time” variable)}$ .

Notes: (1) Test of H2 will be the F-test that the coefficient for the study condition-by-time interaction is zero; (2) Study condition indicator main effect is omitted based on assumption of equal rates at randomization as discussed above; (3) For this hypothesis, “time” is a binary variable indicating assessment at 3 months post-treatment versus assessment at randomization; (4) The “covariates” terms represent adjustment for age, race, gender, Charlson comorbidity index score, chronic somatic illness category and other potential confounders found to be significantly different at randomization, (5) We have included a “site” term to adjust for site differences.

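### Both arms are delivered in groups, but the stated H1 and H2 models have no treatment-group term and neither power calculation allows for within-group correlation, so the tests are anti-conservative if outcomes correlate within groups

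*Protocol*

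**What the plan says.** **Delivery.** Under Living Well (Experimental Condition): "Living Well will be implemented as a 12 session small-group intervention (4-8 persons"), weekly for three months, then monthly group boosters. Under Medical Illness Education and Support Group (Comparison Condition): "The comparison condition will be a once-weekly support and education group", each led by one professional. The size of the comparison groups is not stated.

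**H1 model (Data Analysis).** The fixed terms are site, covariates, condition, time and condition by time. Note 3 adds: "A random intercept and random slope (coefficient for time) will also be specified for the model". H3 and H4 use parallel models, and H5 uses the H1 model itself.

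**H2 model (Data Analysis).** For ER use, "we will use a random intercept mixed effects model since this outcome is assessed at only 2 time points". The fixed terms are site, covariates, time and condition by time.

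**Power (Sample Size).** For ER visits, "the above calculation is based on a basic z-test of proportions", and the text adds: "This calculation is conservative -- we would actually have power equal to .80 to detect a smaller difference", because the analysis model is more powerful. For the SF-12 the inputs are 110 per arm after 12% loss, an effect size of .40 and a correlation of .50 between repeated measurements, with the result that "we would have power = .89 to detect an effect size equal to .40". No ICC, design effect or group inflation appears in either.

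**The concern.** Participants are randomized individually but then share a group, its leaders and each other's company for three months or more. Peer modeling and support are part of how Living Well is meant to work, so outcomes within a group may become correlated after randomization. A model that treats group members as independent then understates the standard error of the treatment effect. That raises the type I error on both primary outcomes and on the secondary outcomes that reuse the H1 model.

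The random effects in the stated models are most naturally read as participant-level: one is a slope over assessment times, and the other is justified by the number of assessments per person. The fixed site term removes differences between sites. It does not absorb correlation among members of one group within a site.

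Because the protocol writes out the equations, the random effects and the power basis, this concerns what it states and not detail left to a later plan.

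**Working it through.** **Inputs from the protocol:** ER rates 10.7% and 25%, two-sided alpha .05, power .80, 125 per arm; SF-12 power .89; Living Well groups of 4 to 8.

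**Assumed, not in the protocol:** ICC of .01, .05 and .10; the same group size in both arms.

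**1. Reproduce the stated sample size.** Mean rate = (.107 + .25)/2 = .1785; difference d = .143. The pooled two-proportion z-test needs n = [1.96·√(2·.1785·.8215) + .8416·√(.107·.893 + .25·.75)]² / .143² = 111.4 per arm. With continuity correction, n = (111.4/4)·[1 + √(1 + 4/(111.4·.143))]² = 125.0 per arm. This matches the stated 250 exactly, so that figure assumes independence. At 125 per arm, power is .800 with the correction and .844 without.

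**2. Design effect.** DE = 1 + (m − 1)·ICC. For m = 6: 1.05, 1.25, 1.50.

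**3. Type I error of the unadjusted test.** 2·[1 − Φ(1.96/√DE)]. For m = 6 and ICC .05: 1.96/√1.25 = 1.753, giving .080.

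| Group size | ICC .01 | ICC .05 | ICC .10 |
|---|---|---|---|
| 4 | .053 | .068 | .086 |
| 6 | .056 | .080 | .110 |
| 8 | .058 | .092 | .133 |

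Simulated t-tests on clustered data (18 groups of 6 per arm) gave .078 at ICC .05 and .107 at .10. Simulations of the stated model forms with no true effect, groups of about 6, and site and covariates left out, rejected .046/.073/.108 (H1) and .051/.073/.106 (H2) at the three ICCs, against .046 at ICC 0. At ICC .01 the inflation is within simulation error.

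**4. ER power, groups of 6.** Under the null the standard error is s0 = √(2·.1785·.8215/125) = .0484; under the alternative it is s1 = √[(.107·.893 + .25·.75)/125] = .0476.
- Unadjusted test, true variance inflated: Φ[(d − 1.96·s0)/(s1·√DE)].
- Group-adjusted test: the same z-test at 125/DE per arm.
- The continuity-corrected versions also subtract 1/n from d, with n = 125 or 125/DE.

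| ER test | ICC 0 | .01 | .05 | .10 |
|---|---|---|---|---|
| Unadjusted, no correction | .844 | .838 | .817 | .795 |
| Unadjusted, corrected | .800 | .794 | .774 | .754 |
| Group-adjusted, no correction | .844 | .83 | .76 | .68 |
| Group-adjusted, corrected | .80 | .78 | .69 | .60 |

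**5. SF-12 power, groups of 6, taking the stated .89 as given.** Its noncentrality is 1.960 + 1.227 = 3.187. Group-adjusted, Φ(3.187/√DE − 1.96) = .875/.813/.739. Unadjusted, Φ(1.227/√DE) = .884/.864/.842.

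**6. What the ER model might recover.** Without continuity correction, the adjusted test keeps .80 up to DE = 125/111.4 = 1.122, which for groups of 6 is an ICC of about .024. Beyond that, if using the baseline cuts the variance by the factor 1 − ρ², holding .80 needs ρ = √(1 − 1.122/DE): about .32 at ICC .05 and .50 at ICC .10. This is an approximation.

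**7. Standard errors after adjustment.** √DE = 1.02, 1.12, 1.22 for groups of 6.

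**The case against.** **The ICC may be small.** This stands. The protocol gives no value, and at .01 nothing of consequence changes. ER use comes from charts and may cluster less than self-reported functioning. Non-attenders stay in the intent-to-treat analysis, which may dilute a group's shared influence. If only Living Well clusters, DE averages with 1 and the type I error for groups of 6 is about .053/.065/.080. None of this gives a reason to assume zero.

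**The planned power is hardly harmed.** This stands for the analysis as written. A reader might infer that ER power drops to .69 or .60 under the plan. It does not: those figures belong to a group-adjusted test. Under the stated, unadjusted analysis the main harm is to type I error.

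**The ER calculation really is conservative.** A reader might infer that this claim is false. The documents do not show that. The continuity correction leaves slack, and a model using baseline ER status may gain more. The claim is incompletely justified, because it counts the model's gain and leaves out the clustering loss.

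**The level of the random effects is not named.** Correct. Participant level is the likely reading, not stated text. On any reading, no treatment-group term appears.

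**Facilitators may cluster too.** A reader might infer this from fidelity monitoring, where "Ratings will be completed by an independent rater from a randomly selected 25% of each peer/provider pair" is sampled. That is quality control, and the planned link between fidelity and outcomes is exploratory. Neither is evidence of correlation by facilitator, and the number of facilitators is not given.

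**Conclusion.** The point holds in conditional form. Both arms are group-delivered, the stated H1 and H2 models name no treatment-group term, and neither power calculation allows for within-group correlation. If that correlation is positive, the direction is certain: the stated tests are anti-conservative.

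The size rests on an assumed ICC and an assumed comparison-group size. For groups of 6 the type I error is about .056/.080/.110 at ICC .01/.05/.10; over groups of 4 to 8 it runs from .053 to .133. This is negligible at the low end and material from about .05. The documents do not establish which end applies, so they do not support saying that the error rate is in fact inflated by a given amount, or that the trial is underpowered. The change should be made because the omission is plain and the correction to the analysis is cheap.

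**What to change.** 1. Record the assigned treatment group for every randomized participant, including those who never attend. This is hard to reconstruct later.
2. In H1 and the models for H3 to H5 that follow it, add a treatment-group random effect acting on the post-randomization time points, with small-sample degrees of freedom. The randomization interview takes place before the groups start (Cost/Payment), so it should carry no group effect.
3. For ER use, apply the same term. The assumed rates imply only about 125·.107 + 125·.25 ≈ 45 participants with a visit after randomization, so pre-specify cluster-robust standard errors by treatment group, with a small-sample correction, if the term cannot be estimated.
4. Restate both power figures as those of the group-adjusted test over a stated range of ICC and group size, including the comparison arm.
5. Qualify the statement that the ER calculation is conservative.
6. Optionally, add a sensitivity analysis clustered on facilitator.

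**Cost.** One data field and revised wording. No extra patients are needed if the power is restated, but standard errors widen by about 2%, 12% and 22% at ICC .01, .05 and .10 (groups of 6), and the stated power becomes less favourable. Keeping the stated ER power instead would take more patients: 125·DE per arm, which is 314 in total for groups of 6 at ICC .05.
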